1.0 INTRODUCTION

The treatment of patients with high grade gliomas remains a challenge for modern therapy. The prognosis for these patients is poor; the median survival time after diagnosis and treatment is less than 1 year [1, 2] and may be linked to the completeness of tumor removal. [3-6]. A recent study of 416 patients with glioblastoma multiforme (GBM) indicates that resection of 89% of the tumor volume is necessary to improve survival and a significant survival advantage of 4.2 months was associated with resection of 98% or more of the tumor volume, compared with resection of less than 98% [7]. However, the highest possible degree of tumor resection is often limited by the surgeon's ability to distinguish residual tumor tissue from surrounding brain tissue under conventional white light surgical microscope illumination [8]. For these reasons, methods enabling better intraoperative discrimination of viable tumor borders may be valuable.

Fluorescence imaging may, potentially, enhance the contrast of viable tumor borders. Although administration of fluorescent markers to enhance contrast of malignant gliomas is not new [9, 10, 11], marking tumors with 5-amino levulinic acid (ALA) is conceptually different from other investigations. ALA is not itself fluorescent but is metabolized into the strongly fluorescent proto-porphyrin IX (PpIX) by a number of malignant tumors *in situ* through enzymes of the heme-biosynthesis pathway [12]. This may avoid pitfalls when a fluorescent marker is administered directly, such as leakage from the tumor into surrounding normal brain tissue [13].

ALA-PpIX fluorescence imaging has previously been investigated at St. Michael's Hospital and the University Health Network, Toronto Cancer Institute [Drs. [name] and [name]]. These studies examined the utility of ALA for detection and photodynamic therapy (PDT) of dysplasia in patients with Barrett's disease of the esophagus.

2.0 OBJECTIVES

2.1 PRIMARY AIM

Our primary *long-term goal* is to improve the completeness of surgical resection of malignant brain tumor through image-guided fluorescence localization. We hypothesize that the use of qualitative fluorescence imaging and point PpIX concentration quantification will enable more complete tumor resection than normal direct (i.e., white light) visualization, and thereby improve patient survival [7].

2.2 PRIMARY OBJECTIVE

Primary objective: As a first step, we will assess 2 doses of 5-ALA, 10mg/kg and 20 mg/kg, to determine the optimum ALA dose in terms of both sensitivity and specificity for residual tumor. We will compare residual tumor detection by both *in vivo* qualitative and quantitative fluorescence imaging using histology of the biopsied tissue as the gold standard.

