4.4.2 LIGHT SENSITIVITY PRECAUTIONS

Before ALA administration, patients will be given verbal and written instructions for protection from sunlight by the staff surgeon or his delegate (see Section 4.7.1). It should be noted that these patients are hospitalized following surgery, so that there is in practice a very small possibility of their being exposed to bright sunlight outdoors. Nursing staff in the recovery room and on the ward will be instructed regarding the need to avoid accidental exposure to bright light in the first 24 hours.

4.4.3 .PATIENT GROUPS AND NUMBERS AND ALA DOSE

This clinical trial has ALA dose at 2 levels (10 and 20 mg/kg) and ALA administration time at 1 time point (3h). Consenting patients scheduled for surgery will be assigned to primary or recurrent arm based on clinical presentation, are then randomly assigned to one of two groups (for dose assignment) within each of the two arms of the study. Sample sizes of the 4 patient groups with two ALA dose levels are listed in the table below:

Table 3: Study Design and Sample Size

	Administration Time	
	3 hours New D _x	3 hours Recurrent D _x
10 mg/kg	30	30
20 mg/kg	30	30

For both patients with new and recurrent disease, biopsies will be taken at up to six sites identified by the surgeon: in the tumor center, tumor edge, area surrounding the tumor (if safe), areas seen to fluoresce intraoperatively and an area with MR enhancement outside

the tumor region (if this can be accomplished safely). Prior to collecting these biopsies readings will be taken at the biopsied location with the PpIX point probe by the surgeon. For each of the 6 biopsies, they will be divided into 3 parts and distributed for further analysis as follows: one portion will be sent to the pathologist for assessment of tumor percentage, one portion will be evaluated by the Division of Biophysics at the University of Toronto for PpIX concentration and the other for assessment of fluorescence.

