5.2 DATA ANALYSIS

5.2.1 FLUORESCENCE INTENSITY LEVELS VS. HISTOPATHOLOGY

The data sets will be collated into the 4 study groups (2 ALA doses and 2 study arms-- i.e., newly diagnosed and recurrent diagnosis) for analysis purposes.

Histopathology of the 1st part of the biopsies, performed by a single experienced neuropathologist (**i.e., [name]**) will be used as the gold standard. The white-light, fluorescence images, and intra-operative PpIX concentration readings will be compared to assess the sensitivity and specificity for biopsy-confirmed visible tumor.

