8.0 STATISTICAL CONSIDERATIONS

8.1 STATISTICAL ANALYSIS PLAN

Primary objective: We will assess 2 doses of 5-ALA, 10mg/kg and 20mg/kg, to determine the optimum ALA dose in terms of both sensitivity and specificity for residual tumor. The endpoint will be correspondence between intensity of *in vivo* fluorescence and PpIX concentration and the pathologist's quantification of tumor in biopsy specimens, e.g. percent tumor present. Receiver operating characteristic (ROC) curves will be calculated for each of the 2 combinations of ALA dose to estimate a level of fluorescence that distinguishes residual tumor from normal tissue with large true positive fraction (TPF) and small false positive fraction (FPF). A joint 95% confidence region for TPF FPF will be calculated, using $\alpha^*=1-\sqrt{1-\alpha}=0.975$ and univariate confidence limits for the individual probabilities. Having chosen the cut-points for each of the 4 combinations, positive and negative predictive values and diagnostic likelihood ratios will be calculated to describe the characteristics of each [18].

To compare the test characteristics of each ALA dose and to assess how the test characteristics are affected by demographic, disease, and surgical characteristics we will

fit multivariable generalized mixed models to tumor and normal biopsy specimens using robust standard errors to account for the correlation of samples taken from the same individual.

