Secondary Objective: We will assess the correlation between the recorded *in vivo* qualitative assessment of fluorescence signal from the neurosurgeon with the post-surgical (i.e., *ex vivo*) absolute PpIX concentration detected in *ex vivo* tissue biopsies. The surgeon will subjectively score the intra-operatively observed fluorescence level as follows: 0, no fluorescence, 1, low fluorescence, 2, moderate fluorescence, or 3, high fluorescence [after 16]. We will first graph fluorescence against each PpIX concentration measurement (intraoperative and *ex vivo*) to evaluate the shape of the relationship. Additionally we will calculate a Spearman's correlation coefficient with 95% confidence interval to assess the correlation between fluorescence against each PpIX concentration measurement (intraoperative and *ex vivo*). The sensitivity and specificity of these observations will be determined [after 16], where the sensitivity of observable intraoperative PpIX fluorescence is the probability of observable intraoperative fluorescence given the presence of tumor cells in the tissue and specificity is the probability of no observable intraoperative fluorescence given that there are no tumor cells in the tissue [16]. We will also explore whether dose, patient, and disease characteristics affect the strength of the relationship between these measurements using multivariable generalized mixed models.

Tertiary Objective: To determine the association between the presence of fluorescence in the surgical cavity and the post-operative image enhancement on MRI. This includes the relationship between the amount and location of residual tumor detected by fluorescence, PpIX concentration, and intra-operative frameless stereotaxy following maximal resection versus the amount and location of tumor imaged post-operatively via CT and/or MRI. Assessment of agreement between fluorescence, intra-operative PpIX concentration, and MR intensity will be explored using the radiologist's assessment of MR intensity, measured on an ordinal scale. A multivariable ordinal logistic model will be fitted to assess the strength of the relationship and whether dose, patient or disease characteristics affect the relationship.

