8.2 SAMPLE SIZE AND STATISTICAL POWER

Our study is powered appropriately for determination of the primary objective which involves the assessment of 2 doses of 5-ALA, 10mg/kg and 20mg/kg, to determine the optimum ALA dose in terms of both sensitivity and specificity for residual tumor. We calculate the total sample size for 80% power at the 0.05 significance level, given that the sensitivity will decrease by 15% with decreasing ALA dose within patient group (i.e. newly diagnosed or recurrent). Therefore our null hypothesis is that the sensitivity of the 10mg/kg dose is less than or equal to 15% different from the 20 mg/kg dose and the

alternative hypothesis is that the sensitivity of the 10mg/kg dose is greater than 15% different from the 20 mg/kg dose. We also take into account having multiple biopsies per individual on study. The total sample size per group per dose is as follows:

The primary objective of this Phase II study is to estimate and compare the combined diagnostic accuracy of in-vivo qualitative assessment of fluorescent signal in detecting residual tumor when used by the neurosurgeon using 2 doses of 5-ALA: 10 mg/kg and 20 mg/kg. The in-vivo qualitative assessment by the neurosurgeon will be coded on an ordinal scale ranging from 0 (no signal) to 3 (highest signal), as was done in a similar study reported by Roberts et al (J Neurosurg 2010 Apr 9, epub ahead of print) using a dose of 20 mg/kg in newly diagnosed gliomas. As in Roberts et al, we assume a score of 1 or higher will be considered positive. In the study by Roberts et al (2010) the reported sensitivity and specificity were 0.75 and 0.71, respectively, using the histopathologic reading as gold standard. In this study, because having high sensitivity and specificity are both important in terms of avoiding false negatives (which would involve not removing residual tissue) and false positives (removing normal tissue), the Youden index, defined as Sensitivity + Specificity -1 will be used as an overall measure of diagnostic accuracy. This study is designed so that if the dose levels of 10 and 20 mg/kg have true Youden indices that differ by 0.10 or more, then the probability is 80% or higher that the observed Youden index will be higher for the group with the higher actual index, i.e., the probability of selecting the correct dose level based on observed Youden indices will be 80% or higher.

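### Section 8.1 has no analysis for the promised qualitative-versus-quantitative comparison, and the cuts it implies could flatter the quantitative marker by about 0.03 to 0.05 in Youden index

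*Combined protocol and SAP*

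**What the plan says.** Section 2.2 sets dose choice as the primary objective. It then says that detection will be compared by "qualitative and quantitative fluorescence imaging using histology of the biopsied tissue as the gold standard". Section 5.2.1 lists white-light images, fluorescence images and probe readings, and says that the "intra-operative PpIX concentration readings will be compared to assess the sensitivity and specificity for biopsy-confirmed visible tumor".

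Section 8.1 plans the following:

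- Under the primary objective, ROC curves are used "to estimate a level of fluorescence that distinguishes residual tumor from normal tissue". Predictive values and likelihood ratios follow: "Having chosen the cut-points for each of the 4 combinations". No rule for choosing the cut is given beyond a large true positive fraction (TPF) and a small false positive fraction (FPF). No validation step is described.
- The mixed models are there "To compare the test characteristics of each ALA dose and to assess how the test characteristics are affected by demographic, disease, and surgical characteristics". No term for modality is named.
- Under the secondary objective, the sensitivity of the surgeon's reading "is the probability of observable intraoperative fluorescence given the presence of tumor cells in the tissue", which in effect means a score of 1 or higher. A Spearman correlation between score and PpIX is also planned.

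Section 8.2 makes the score cut explicit: "we assume a score of 1 or higher will be considered positive". The two readings belong to the same biopsy. Section 4.4.3 (Patient Groups and Numbers) says: "Prior to collecting these biopsies readings will be taken at the biopsied location with the PpIX point probe by the surgeon".

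**The concern.** The plan announces a comparison and then supplies only separate summaries. A Spearman coefficient shows whether score and PpIX move together, not which of them finds tumor better. The robust standard errors deal with several biopsies from one patient, not with two markers read on one biopsy.

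The summaries left to set side by side are not like for like. A cut fixed beforehand gives an honest estimate of sensitivity and specificity. A cut picked on the same biopsies, and then judged on them, gives an optimistic one. If the two are placed together, the quantitative marker starts with an advantage that has nothing to do with accuracy. At stake is the trial's answer on whether measuring PpIX adds anything to the surgeon's eye. Section 1.0 makes that question matter: it criticises earlier work as subjective and not quantitative, and says that the group is developing the point probe.

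**Working it through.** **1. The plan's own figure.** Section 8.2 sizes each dose-by-stratum cell at 30 for an 80% chance of picking the better dose on the score, when the Youden indices differ by 0.10. The formula is n = z(0.80)² × Σp(1−p) × (1+2ρ)/3 ÷ 0.10². Take the least favourable row: 0.65 and 0.70 against 0.55 and 0.70, with ρ = 0.2.

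- Σp(1−p) = 0.2275 + 0.21 + 0.2475 + 0.21 = 0.895.
- n = 0.7083 × 0.895 × 1.4/3 ÷ 0.01 = 29.6, so 30, as printed.

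All 24 table entries reproduce to within one patient. At n = 30 and ρ = 0.2 the selection probability is 0.802 to 0.825 across the rows. This calculation covers dose choice on the score; no stated figure covers the comparison of modalities.

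**2. Optimism from choosing the cut on the data.** Inputs from section 8.2: 3 tumor and 3 normal biopsies per patient, and 30 patients per cell, or 30 + 30 = 60 per dose. Assumptions: equal-variance binormal markers, a cut that maximises Youden, and a patient effect with correlation 0.1 or 0.3 on the underlying scale (about 0.06 or 0.18 between binary results). For a true maximum Youden of 0.45 the separation is 2Φ⁻¹((1+0.45)/2) = 1.196. Mean in-sample Youden at the chosen cut minus the true maximum, from 2000 runs per setting:

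| True Youden | 30 patients | 60 patients |
|---|---|---|
| 0.35 | 0.051 | 0.030-0.031 |
| 0.45 | 0.043-0.046 | 0.027-0.028 |

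A head-to-head simulation (4000 runs per setting) used two markers, both with true Youden 0.45. The score cut was fixed at its optimum, and the correlation between markers was 0, 0.5 or 0.8.

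- The quantitative marker was ahead by 0.041-0.045 at n = 30 (about 0.494 against 0.45).
- It was ahead by 0.026-0.030 at n = 60 (about 0.479 against 0.45).
- It looked better in 65-79% of trials, although its true Youden at the chosen cut was only 0.434-0.441.

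**3. Size against the noise.** With the plan's variances at n = 30 and ρ = 0.2:

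- SE(sensitivity) = √(0.75×0.25×1.4/90) = 0.054.
- SE(specificity) = √(0.70×0.30×1.4/90) = 0.057.
- SE(Youden) = √(0.054² + 0.057²) = 0.079.

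For a difference on the same biopsies, SE = √(2(1−φ)) × 0.079, where φ is an assumed correlation between markers. For φ = 0.3, 0.5 and 0.7 this gives 0.093, 0.079 and 0.061, so 95% half-widths of 0.18, 0.15 and 0.12. The bias is therefore about a quarter (0.041/0.182) to two fifths (0.045/0.119) of the half-width.

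**4. Which remedies work.** These were tried on markers of equal accuracy.

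- Comparing TPF at the score's own FPF, on the same biopsies: bias of at most 0.006.
- Comparing raw areas under the curve: not neutral. Cutting one and the same marker down to four levels lowered its area by about 0.02-0.05 (for example from 0.801 to 0.753-0.781).
- Re-choosing the cut inside each bootstrap resample and judging it on that resample: optimism stays. With true Youden 0.45 and n = 30, the in-sample mean was 0.499 and the bootstrap mean 0.521.

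**The case against.** The strongest reply is that no head-to-head comparison was ever planned. The sentence in section 2.2 can be read as assessing each dose by both methods against histology. Sections 8.1 and 8.2 restate the primary objective as dose choice, and the trial is sized for that alone. This reading is possible, but section 5.2.1 lists the modalities and says that they will be compared on sensitivity and specificity. The plan should say which is meant.

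The second reply is that section 8.1 speaks of a level of fluorescence without limiting the ROC step to the quantitative measure. The 0-3 score could have an ROC curve too, and its explicit cut stands in the sample-size section. This also stands in part: the asymmetry is the natural reading, not a stated rule. The size of the bias depends on an assumed criterion for the cut. Section 8.1 mentions both 2 and 4 combinations; if cuts are set per dose, the figure nearer 0.03 applies.

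A reader might also infer that the plan analyses the readings as unpaired and so inflates the standard error, by 1.2 to 1.8 times for a between-marker correlation of 0.3 to 0.7. The documents do not support this. They specify no test of modality, paired or unpaired, and the data remain paired by biopsy. The method paper cited in 8.1 as reference 18 is, by its title, about ROC areas from the same cases, although it is cited there only for predictive values and likelihood ratios.

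**Conclusion.** The concern holds in a limited form. The protocol promises a comparison of qualitative with quantitative fluorescence, and section 8.1 has no analysis for it. The rules that can be read from the plan give unlike figures, and these favour the quantitative marker by about 0.03 (60 patients per dose) to 0.04-0.05 (30 per cell) in Youden index when the two are truly equal. This rests on a binormal model, a cut that maximises Youden, and an ROC step applied to the quantitative measure. The bias is modest beside the uncertainty of the comparison, but it runs in one direction.

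It would be wrong to infer that the dose selection or its sample size is undermined: n = 30 is confirmed for choosing a dose on the score. Nor is it certain that readers would conclude that quantification wins. The 0.10 difference in section 8.2 is a difference between doses, so it is not a yardstick for modalities. The point should be settled before analysis; confidence in it is low because the text is open to other readings.

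**What to change.** State in section 8.1 whether the modalities are formally compared, and whether per dose or per dose and stratum. If they are:

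1. Make the contrast within the same biopsies. Take the score's FPF at 1 or higher, find the quantitative marker's TPF at that FPF, and report the difference from the score's TPF. Give a 95% interval from a bootstrap that resamples whole patients and re-matches the FPF each time.
2. If Youden, predictive values or likelihood ratios at a data-chosen cut are set beside the score, report them cross-validated by patient or corrected for optimism.
3. Do not rest the comparison on a raw difference in area between a four-level score and a continuous marker.
4. Present the result as an estimate. With the plan's variances and n = 30, two-sided power for a true modality difference of 0.10 in Youden is only about 19-38% on paired data (φ 0.3 to 0.7).

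The cost is SAP wording and modest programming, with no new data. Biopsies that lack one of the two readings drop out of the contrast, and any advantage of the quantitative marker will look slightly smaller.

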2.3 SECONDARY OBJECTIVE

Secondary Objective: We will assess the correlation between the recorded *in vivo* qualitative assessment of fluorescence signal from the neurosurgeon with the post-surgical (i.e., *ex vivo*) absolute PpIX concentration detected both intraoperatively and in *ex vivo* tissue biopsies.

2.4 TERTIARY OBJECTIVE

Tertiary Objective: To determine the association between the presence of fluorescence in the surgical cavity and the post-operative image enhancement on MRI. This includes the relationship between the amount and location of residual tumor detected by fluorescence, PpIX concentration, and intra-operative frameless stereotaxy following maximal resection versus the amount and location of tumor imaged post-operatively via CT and/or MRI.

3.0 ELIGIBILITY CRITERIA

3.1 PATIENT ELIGIBILITY CRITERIA

Patients will be eligible for this study if they meet all of the following criteria:

Table 1: Inclusion Criteria

Age	18 years or older
Tumor Pathology	Suspected or confirmed newly diagnosed or recurrent malignant gliomas WHO grade IV
Location	Supratentorial
Resection	Tumor must be judged suitable for resection on the basis of imaging studies.
Consent	Patients must be able to give written, informed consent as approved by the local IRB
Newly Diagnosed Tumors	Patients with newly diagnosed suspected Grade IV glioma who have had not been previously treated with cranial radiation therapy
Recurrent Tumors	Patients with recurrent Grade IV gliomas who have failed cranial radiation therapy

It is the policy of the Case Comprehensive Cancer Center to strive for gender and minority patient participation that represents the population of Northeast Ohio in all clinical investigations. Both men and women of all races and ethnic groups are eligible for this trial.

Grade IV gliomas will likely have a different PpIX uptake and thus fluoresce differently compared to Grade III gliomas [15] therefore, this study will only focus on Grade IV gliomas. However, the grade of the glioma is not certain until surgical resection of the glioma at which point biopsies are taken for histopathological determination of the glioma grade. As a result some patients with Grade III gliomas may be enrolled in this study, but these patients will be excluded from primary analysis. The data obtained from patients with Grade III gliomas will be used to explore differences in fluorescence between Grade III and Grade IV brain tumors. We do not expect that this will result in a statistically significant difference, but only that generate hypothesis for future studies.

3.2 EXCLUSION CRITERIA

Patients will be excluded from participation in the study if they meet any of the following criteria:

Table 2: Exclusion Criteria

Pregnant women or those who are breast feeding
Individuals with history of cutaneous photosensitivity, porphyria, hypersensitivity to porphyrins, photodermatitis, exfoliative dermatitis
Individuals with history of liver disease in last 12 months
Individuals with AST, ALT, ALP, or bilirubin >2.5x normal upper limit any time during the previous 2 months
Individuals with plasma creatinine >180 µmol/L
Individuals who are unable to comply with photosensitivity precautions
Individuals without a probable or expected grade IV glioma

A baseline blood sample will be drawn for creatinine, AST, ALT, ALP, and bilirubin to verify whether or not this exclusion criterion is met.

